4 STUDY DESIGN

4.1 OVERALL DESIGN

A pilot, single-blinded, cluster randomized, pragmatic trial of the SPECTORx intervention.

We will compare outcomes within and across 2 large, multi-office, hospice agencies from Utah and Massachusetts. Within each hospice agency, we will randomize 1 office to intervention and 1 office to attention control. Target enrollment is 30 FCG-patient dyads per agency (n=15 intervention, n=15 control), for a total trial target of n=60 FCG-dyads of patients aged ≥ 65 years, with an estimated life expectancy of >1 month, and polypharmacy (defined as ≥ 5 regularly scheduled daily medications).

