5.5 STRATEGIES FOR RECRUITMENT AND RETENTION

Patient and family caregiver participants will be recruited through the participating home hospice clinical sites. Each site minimally includes a dedicated Site Investigator and Research Assistant capable of enrolling in and conducting the study.

The total enrollment is up to 60 consenting patient-FCG dyads. Within each of the 2 hospice agencies, we will randomize 1 office to intervention and 1 to control status. Target enrollment is 15 FCG-patient dyads at each office (total 30 FCG-patient dyads per hospice agency).

Hospice clinician participants will be recruited at each hospice site. In cooperation with hospice administrative leaders, we will present the study to the hospice clinical teams and invite teams randomized to the intervention to complete the online education training intervention about medication review, education, and deprescribing.

The Site PI will develop study-specific recruitment strategies in consultation with the local hospice administration. Site RA and CRCs and other study staff will attend an introductory training program covering research related-communication, ethics, recruitment planning and implementation.

The screening and recruitment algorithms will be developed for each site, delineating expected processes and highlighting potential hurdles so that effective solutions can be developed. Key messages for the recruitment call/visit, supporting study diagrams, recruiting scripts, strategies for working with

bereaved family members, and simplified consent language will be developed. Tools will be practiced through role plays: refresher role plays will be repeated periodically during the study to ensure quality and consistency. Recruitment metrics will be monitored on a regular basis and will include screening eligibility, study completion, study withdrawal rates; progress will be presented to Site Investigators and staff. If a study site should encounter particular difficulty with enrollment, the study team may conduct a site visit to review obstacles and devise solutions, presenting results for review to the existing study stakeholder panel.

Site specific screening will follow this general scheme, but may be adapted (as described herein) to local workflow procedures to minimize impact on clinical care delivery:

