6.3 MEASURES TO MINIMIZE BIAS: RANDOMIZATION AND BLINDING

Randomization is at the level of the office location within each hospice agency.

Outcomes assessments will be blinded with withholding intervention assignment data from the clinical research coordinator responsible for data collection related to the measurement of patient and family-caregiver outcomes and from the adjudication team responsible for measuring ADE and ADWEs.

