9.4.3 ANALYSIS OF THE SECONDARY ENDPOINT(S)

A secondary goal of this pilot is to estimate preliminary intervention treatment effect size for a large-scale, R01-funded trial. Comparisons will be made between the baseline and follow-up assessments, both within and across intervention and control sites. Descriptive analyses will establish data distributions for continuous outcomes (e.g. FCG Hassles Scale). We will use linear mixed effects models to account for cluster randomization for continuous outcomes. Clusters are hospice agencies, offices within agencies, clinicians within office, and patients within clinicians/nurses. Even with small samples, we can explore the relationship between change in measures (e.g. # PIMs) and FCG/patient factors. Mixed effects models are robust with small sample sizes and adjust for correlations from repeated measures within individuals and from clustering.

Missing Data. Descriptive analyses will characterize missing data frequency and examine associations with key characteristics (e.g. admitting diagnosis, race). Variables associated with missingness will be included in analyses as covariates to account for possible effects from the missing pattern (missing at random). ³⁶

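### Section 9.4.3 calls mixed models robust in small samples without restriction, but the arm effect rests on four randomised offices, for which that statement does not hold (minor)

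*Combined protocol and SAP*

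**What the plan says.** Section 9.4.3 sets the aim: "A secondary goal of this pilot is to estimate preliminary intervention treatment effect size for a large-scale, R01-funded trial". The method follows: "We will use linear mixed effects models to account for cluster randomization for continuous outcomes". The levels are then listed: "Clusters are hospice agencies, offices within agencies, clinicians within office, and patients within clinicians/nurses". Next comes a sentence on participant-level exploration, "Even with small samples, we can explore the relationship between change in measures (e.g. # PIMs) and FCG/patient factors", and directly after it the sentence at issue: "Mixed effects models are robust with small sample sizes and adjust for correlations from repeated measures within individuals and from clustering".

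The number of randomised units comes from the design sections. Section 4.1 has "Within each hospice agency, we will randomize 1 office to intervention and 1 office to attention control", Section 5.5 repeats this, and Section 6.3 confirms the unit: "Randomization is at the level of the office location within each hospice agency". Sections 4.2 and 6.4 also speak of teams being randomised, and Section 4.2 of the hospice, but every count given is a count of offices.

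Section 9.4.3 gives no degrees-of-freedom rule, small-sample correction or interval method for the arm effect. Section 9.4.1 (General Approach) has a heading but no text in the version supplied. Section 10.1.7 names SAS as the analysis software and gives no model settings. Section 9.2 concedes that the trial lacks power for efficacy.

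**The concern.** How well a mixed model behaves in small samples depends on the number of units at the level where the effect varies. A caregiver or patient characteristic varies among 60 dyads. The arm varies only among four offices. The sentence on robustness covers both cases, and it names clustering explicitly.

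With so few offices the between-office variance is barely estimable and is often estimated as zero. The fitted model then makes no allowance for office differences, although it formally includes them. An analyst who relies on the sentence could attach an interval to the effect size that is too narrow, and the R01 trial could be planned on a figure that looks more precise than it is.

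**Working it through.** **Inputs from the documents.** Two agencies, two offices per agency (one per arm), 15 dyads per office (Sections 4.1, 4.2, 5.5, 6.3). The plan's one relevant figure reproduces: 2 × 2 × 15 = 60 dyads. No alpha, SD, ICC or interval is stated for the arm effect, so there is nothing further to reproduce.

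**Degrees of freedom.** Offices minus intercept, agency and arm: 4 − 1 − 1 − 1 = 1. Without agency: 4 − 2 = 2. The 97.5% t quantiles are 12.71 and 4.30, against 1.96 for the normal.

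**Assumptions.** ICC is taken as 0 to 0.10 and refers to the outcome as analysed; for a baseline-to-follow-up comparison it is the office-level ICC of change. One outcome per dyad, total SD 1, complete balanced data, office random, agency fixed, REML with non-negative office variance.

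**True standard error.** Let D1 and D2 be the intervention-minus-control differences in office means within each agency. The estimate is (D1 + D2)/2, with variance V = ICC + (1 − ICC)/n for n dyads per office.

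| ICC | V (n = 15) | SE | 1.96 × SE | 1.96 × SE (n = 10) |
|---|---|---|---|---|
| 0.01 | 0.01 + 0.99/15 = 0.0760 | 0.276 | 0.54 SD | 0.65 SD |
| 0.05 | 0.05 + 0.95/15 = 0.1133 | 0.337 | 0.66 SD | 0.75 SD |
| 0.10 | 0.10 + 0.90/15 = 0.1600 | 0.400 | 0.78 SD | 0.85 SD |

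**Chance that office variance is estimated as zero.** This happens when the office mean square, 15(D1 − D2)²/4 on 1 df, does not exceed the within-office mean square on 4 × 14 = 56 df. The probability is P[F(1,56) ≤ (1 − ICC)/(1 − ICC + 15 × ICC)]. The bounds are 0.99/1.14 = 0.868, 0.95/1.70 = 0.559 and 0.90/2.40 = 0.375, giving 0.645 / 0.542 / 0.457 at ICC 0.01 / 0.05 / 0.10.

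**Coverage of a nominal 95% mixed-model interval** (400,000 simulated trials per setting, 15 dyads per office):

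| ICC | Normal reference | Residual df |
|---|---|---|
| 0 | 95.8% | 96.2% |
| 0.01 | 94.6% | 95.0% |
| 0.02 | 93.5% | 94.0% |
| 0.05 | 90.2% | 90.8% |
| 0.10 | 85.9% | 86.6% |

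With 10 outcomes per office, normal-reference coverage is 94.8 / 91.7 / 88.3% at 0.01 / 0.05 / 0.10. Treating agency as random does not restore it: about 89% and 84% at 0.05 and 0.10 with 15 per office.

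**The 1-df office-summary interval.** (D1 − D2)/2 also has variance V and is independent of the estimate, so the estimate ± 12.71 × |D1 − D2|/2 covers 95% at every ICC. Its width hangs on one random difference. It is narrower than 1.96 × the true SE with probability P(|Z| < 1.96/12.71) = P(|Z| < 0.154) = 0.12, and in those trials it covers only about 60%. Its median half-width at ICC 0.05 is about 2.9 SD.

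**The case against.** Much of the case for the plan stands.

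- **No interval is promised.** Section 9.4.3 plans an estimate. It sets no interval, test or decision rule for the arm effect. Section 9.1 calls the study exploratory and Section 9.2 disclaims power. The harm is therefore conditional on an interval being reported and on offices differing. The disclaimer does not dispose of the point, though: low power is one matter and a standard error that is too small is another.
- **A narrower reading exists.** The sentence follows one about caregiver and patient factors and may have been meant for those. But it names clustering, is not restricted, and shares a paragraph with the effect-size aim, so the text does not limit it.
- **The simulation is simpler than the planned analysis.** The plan has repeated measures and baseline-to-follow-up comparisons, and stable office differences cancel from change scores. The relevant ICC may then be small, and the shortfall with it. The documents give neither ICC.
- **Prescribing the 1-df interval would be a debatable trade.** It can be falsely narrow, and raw office means drop the repeated measures and the missingness covariates that Section 9.4.3 plans.

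A reader might infer that four offices cannot separate the intervention from office differences at all. With two randomised pairs they can, but very imprecisely. A reader might also infer that the sponsor has committed to an invalid interval; no interval is specified, so the documents do not support that.

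**Conclusion.** Minor, and wrong as written. The unrestricted robustness statement does not hold for the arm effect, which has 1 df for between-office variance with agency in the model and 2 without. This takes the office as the randomised unit, as the stated counts do.

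The size of the consequence depends on ICCs that are assumed. A normal or residual-df interval is essentially sound at 0.01 or below, about 5 points short of 95% coverage at 0.05, and about 9 points short at 0.10 (normal reference, 15 dyads per office).

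Only a secondary estimate is touched. The feasibility and acceptability endpoints, analysed descriptively under Section 9.4.2, do not depend on it. Nor does the point count against using mixed models for participant-level exploration.

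**What to change.** In Section 9.4.3:

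1. Limit the robustness sentence to participant-level exploratory associations, or delete it.
2. Report the arm-effect estimate with its uncertainty at stated assumed ICCs, for example the 1.96 × SE half-widths tabulated above at 0.01, 0.05 and 0.10 for the number of dyads achieved, in place of relying on whatever interval the software prints. Say that the ICC refers to the outcome as analysed.
3. State that the arm effect rests on four offices (1 or 2 df), so intervention and office differences can be separated only very imprecisely.

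The 1-df office-summary interval may be added as an optional supplement, with a warning that its width depends on a single difference and is falsely narrow in about 12% of trials. It would also help to use one term for the randomised unit in Sections 4.2, 6.3 and 6.4.

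The cost is wording and analysis specification; enrolment, offices and data collection do not change. The downside is that the stated precision becomes less favourable and depends on ICCs the pilot cannot itself establish.

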9.4.4 SAFETY ANALYSES

Safety reports will be sent to the Safety Officer and Project Officer at every 3 months and will include a detailed analysis of study progress, data and safety issues, including interim analyses as described in 9.4.6.

9.4.5 BASELINE DESCRIPTIVE STATISTICS

1. Baseline characteristics of the patients and family caregivers.

9.4.6 PLANNED INTERIM ANALYSES

1. Recruitment by week/month;
2. Treatment phase of patients & family caregivers (screened, enrolled, follow-up phase);
3. Completeness of data (assessments completed, % of expected forms submitted, % of submitted forms passing edit);
4. Missed assessments and missing information within assessments;
5. Summary of adverse events by type;

6. Summary of adverse events by body system;
7. Summary of actual medication changes;
8. Listing of adverse events (including duration, severity, seriousness, relatedness, action taken, resolution);
9. Descriptive information for each endpoint without statistical testing except at designated interim monitoring points if requested by the DSMB, including # and details of medication changes for each patient during the study;
10. Compliance information (completion of intervention training by clinical staff); and
11. Quality control analyses.

9.4.7 SUB-GROUP ANALYSES

Analyses by intervention and control status.

9.4.8 TABULATION OF INDIVIDUAL PARTICIPANT DATA

9.4.9 EXPLORATORY ANALYSES

10 SUPPORTING DOCUMENTATION AND OPERATIONAL CONSIDERATIONS

10.1 REGULATORY, ETHICAL, AND STUDY OVERSIGHT CONSIDERATIONS

10.1.1 INFORMED CONSENT PROCESS

10.1.1.1 CONSENT/ASSENT AND OTHER INFORMATIONAL DOCUMENTS PROVIDED TO PARTICIPANTS

To alleviate the burden of obtaining written consent from these typically home-bound patients and their family caregivers, we will use a telephone based consent procedure. That is, we will obtain a waiver of written documentation of informed consent for this minimal risk participation study for family caregivers and patients, since their involvement requests only access to medical records and completion of telephone questionnaires.

If a patient and family caregiver a potentially interested in study participation, they will be given a Fact Sheet by the hospice staff that summarizes the relevant information about the study, including the risks, benefits, and rights as a study participant. Hospice staff will not answer questions about the study consent, but will refer all questions to trained study staff who will be scheduled to call the patient within 1 week of referral to the study staff. The fact sheets will describe the study in detail the study intervention, study procedures, and risks.

Potentially eligible patients will be referred to the study team. To minimize burden of making a unnecessary study enrollment calls to ineligible patients, we will request a HIPAA waiver for medical record review for the express purpose of confirming eligibility by the study team. If confirmed to be eligible, the study team will call the patient and family caregiver to explain the study, answer any question about participation and the fact sheet, and to obtain telephone recorded consent.

Persons with dementia will be given the opportunity to consent for themselves because cognitive impairment is not always associated with the lack of capacity to provide informed consent to participate in research. Study staff will explain the study and assess capacity to consent based on the standard decision-making capacity criteria of: (a) ability to communicate a yes or no decision; (b) ability to understand relevant information; (c) ability to appreciate the situation and its likely consequences; and (d) ability to manipulate information rationally. If the patient is unable to meet all 4 of these criteria, we will obtain consent from a legally authorized representative (LAR). Further, study staff will obtain consent from the LAR for persons with a documented dementia severity of FAST 6 or greater as this indicates severe dementia with limited speech ability, or individuals has been ruled incompetent by a court of law or with documentation by a qualified practitioner in the medical record that the individual lacks capacity to make the decision to participate in the proposed study.

Utah and Massachusetts hospice sites will provide lists of individuals who are authorized to consent when the patient is unable to consent on their own behalf. In Utah this includes any married person for

a spouse and any person 18 years of age or older for his or her parent who is unable to reason of age, physical or mental condition, to provide such consent. In Massachusetts this includes a health care agent or guardian.

The LAR will be provided with the description of the research study and informed of their role and obligation to protect the rights and welfare of the patient participant. The LAR must be informed that the obligation as a surrogate decision maker is to try to determine what the participant would decide if the participant were able to make such decisions. In the case of this study, the patient's participation would be limited to providing HIPAA waiver for access to the medical record for data collection.

The following consent materials are submitted with this protocol.

- Study fact sheet for patients
- Study fact sheet for family caregivers
- Telephone consent script
- Assessing Capacity to Consent Form

10.1.2 STUDY DISCONTINUATION AND CLOSURE

This study may be temporarily suspended or prematurely terminated if there is sufficient reasonable cause. Written notification, documenting the reason for study suspension or termination, will be provided by the suspending or terminating party to study participants, the investigator and the funding agency (NIA). If the study is prematurely terminated or suspended, the Principal Investigator (PI) will promptly inform study participants, the IRB, and sponsor and will provide the reason(s) for the termination or suspension. Study participants will be contacted, as applicable, and be informed of changes to study visit schedule.

Circumstances that may warrant termination or suspension include, but are not limited to:

- Determination of unexpected, significant, or unacceptable risk to participants
- Demonstration of efficacy that would warrant stopping
- Insufficient compliance of study staff to the protocol (i.e., significant protocol violations)
- Data that are not sufficiently complete and/or evaluable
- Determination that the primary endpoint has been met
- Determination of futility

The study may resume once concerns about safety, protocol compliance, and data quality are addressed, and satisfy the funding agency, sponsor, IRB, or Safety Officer.

10.1.3 CONFIDENTIALITY AND PRIVACY

Participant confidentiality and privacy is strictly held in trust by the participating investigators, their staff, the safety and oversight monitor(s), and the sponsor(s) and funding agency. This confidentiality is extended to the data being collected as part of this study. Data that could be used to identify a specific study participant will be held in strict confidence within the research team. No personally-identifiable information from the study will be released to any unauthorized third party without prior written approval of the sponsor/funding agency.

All research activities will be conducted in as private a setting as possible.

The study monitor, other authorized representatives of the sponsor, representatives of the Institutional Review Board (IRB), may inspect all documents and records required to be maintained by the investigator, including but not limited to, medical records (office, clinic, hospice or hospital) and pharmacy records for the participants in this study. The clinical study site will permit access to such records.

The study participant's contact information will be securely stored at each clinical site for internal use during the study. At the end of the study, all records will continue to be kept in a secure location for as long a period as dictated by the reviewing IRB, Institutional policies, or sponsor requirements.

Study participant research data, which is for purposes of statistical analysis and scientific reporting, will be transmitted to and stored at the University of Massachusetts Medical School Data Coordinating Center. This will not include the participant's contact or identifying information. Rather, individual participants and their research data will be identified by a unique study identification number. The study data entry and study management systems used by clinical sites and by the University of Massachusetts Medical School Data Coordinating Center research staff will be secured and password protected. At the end of the study, all study databases will be de-identified and archived at the the University of Massachusetts Medical School Data Coordinating Center.

Measures Taken to Ensure Confidentiality of Data Shared per the NIH Data Sharing Policies It is NIH policy that the results and accomplishments of the activities that it funds should be made available to the public (see <https://grants.nih.gov/policy/sharing.htm>). The PI will ensure all mechanisms used to share data will include proper plans and safeguards for the protection of privacy, confidentiality, and security for data dissemination and reuse (e.g., all data will be thoroughly de-identified and will not be traceable to a specific study participant). Plans for archiving and long-term preservation of the data will be implemented, as appropriate.

Certificate of Confidentiality

To further protect the privacy of study participants, the Secretary, Health and Human Services (HHS), has issued a Certificate of Confidentiality (CoC) to all researchers engaged in biomedical, behavioral, clinical or other human subjects research funded wholly or in part by the federal government. Recipients of NIH funding for human subjects research are required to protect identifiable research information from forced disclosure per the terms of the NIH Policy (see <https://humansubjects.nih.gov/coc/index>). As set forth in 45 CFR Part 75.303(a) and NIHGPS Chapter 8.3, recipients conducting NIH-supported research covered by this Policy are required to establish and maintain effective internal controls (e.g., policies and procedures) that provide reasonable assurance that the award is managed in compliance with Federal statutes, regulations, and the terms and conditions of award. It is the NIH policy that investigators and others who have access to research records will not disclose identifying information except when the participant consents or in certain instances when federal, state, or local law or regulation requires disclosure. NIH expects investigators to inform research participants of the protections and the limits to protections provided by a Certificate issued by this Policy.

